7.2 Lost to follow-up

A subject will be considered potentially lost to follow-up if the subject fails to return for scheduled visits and is unable to be contacted by the study site.

The following actions must be taken if a subject fails to return to the clinic for a required study visit:

- The site must attempt to contact the subject and reschedule the missed visit as soon as possible and counsel the subject on the importance of maintaining the assigned visit schedule.
- Before a subject is deemed lost to follow-up, the Investigator or designee must make every effort to regain contact with the subject or next of kin by, eg, repeat telephone calls,

certified letter to the subject's last known mailing address or local equivalent methods. These contact attempts should be documented in the subject's medical record.

- Efforts to reach the subject should continue until the end of the study. Should the subject be unreachable at the end of the study, the subject should be considered to be lost to follow-up with unknown vital status at end of study and censored at latest follow-up contact.

7.3 Withdrawal from the study

A subject may withdraw from the study (eg, withdraw consent), at any time (IP and assessments) at the subject's own request. There will be no penalty or loss of benefit to the subject.

A subject who considers withdrawing from the study must be informed by the Investigator about modified follow-up options (eg, telephone contact, a contact with a relative or treating physician, or information from medical records). Circumstances of withdrawal will be documented in writing by the Investigator.

If the subject withdraws consent for disclosure of future information, the sponsor may retain and continue to use any data collected before such a withdrawal of consent.

If a subject withdraws from the study, the subject may request destruction of any samples taken, and the Investigator must document this in the site study records.

A subject who withdraws consent will always be asked about the reason(s) and the presence of any AE. The Investigator will follow up with subjects as medically indicated.

See SoA ([Table 1](#) and [Table 2](#)), for data to be collected at the time of study discontinuation and follow-up and for any further evaluations that need to be completed.

8 STUDY ASSESSMENTS AND PROCEDURES

Study procedures and their timing are summarized in the SoA ([Table 1](#) and [Table 2](#)).

The Investigator ensures the accuracy and completeness of eCRFs, including eligibility and timeliness of the data recorded and of the provision of answers to data queries according to the Data Management Plan. The Investigator will sign the completed eCRFs. A copy of the completed eCRFs will be archived at the study site.

Immediate safety concerns should be discussed with the sponsor immediately upon occurrence or awareness to determine if the subject should continue or discontinue study treatment.

Adherence to the study design requirements, including those specified in the SoA ([Table 1](#) and [Table 2](#)), is essential and required for study conduct.

All screening evaluations must be completed and reviewed to confirm that potential subjects meet all eligibility criteria. The Investigator will maintain a screening log to record details of all subjects screened and to confirm eligibility or record reasons for screening failure, as applicable.

Procedures conducted as part of the subject's routine clinical management (eg, blood count) and obtained before signing of the ICF may be utilized for screening or baseline purposes provided the procedures met the CSP-specified criteria and were performed within the time frame defined in the SoA.

The maximum amount of blood collected from each subject over the duration of the study, including any extra assessments that may be required, will not exceed 150 mL. Repeat or unscheduled samples may be taken for safety reasons or for technical issues with the samples.

8.1 Efficacy assessments (not applicable)

8.2 Safety assessments

Planned time points for all safety assessments are provided in the SoA ([Table 1](#) and [Table 2](#)).

8.2.1 Clinical safety laboratory assessments

The clinical chemistry, hematology, and urinalysis will be performed at a local laboratory at or near to the study site.

See [Table 11](#) for the list of clinical safety laboratory tests to be performed and to the SoA ([Table 1](#) and [Table 2](#)) for the timing and frequency. All CSP-required laboratory assessments, as defined in the table, must be conducted in accordance with the laboratory manual and the SoA ([Table 1](#) and [Table 2](#)).

The Investigator should make an assessment of the available results with regard to clinically relevant abnormalities. The laboratory results should be signed, dated, and retained at center as source data for laboratory variables.

For information on how AEs based on laboratory tests should be recorded and reported, see [Section 8.3.7](#).

Additional safety samples may be collected and analyzed if clinically indicated at the discretion of the Investigator. The date of collection will be recorded on the appropriate CRF.

Table 11 Laboratory safety variables

Hematology (whole blood)	Clinical Chemistry (serum or plasma)
White blood cell (WBC) count	Alanine aminotransferase (ALT)
Red blood cell (RBC) count	Aspartate aminotransferase (AST)
Hemoglobin (Hb)	Alkaline phosphatase (ALP)
Hematocrit (HCT)	Gamma glutamyl transpeptidase (GGT)
Mean corpuscular volume (MCV)	Total bilirubin
Mean corpuscular hemoglobin (MCH)	Unconjugated bilirubin
Mean corpuscular hemoglobin concentration (MCHC)	C-reactive protein (CRP)
Neutrophils absolute count	Blood Urea Nitrogen
Monocytes absolute count	Creatinine
Eosinophils absolute count	Glucose (fasting)
Basophils absolute count	Albumin
Platelets	Phosphate
Reticulocytes absolute count	Potassium Calcium
Urinalysis	
Glucose	Bicarbonate
Protein	Thyroid stimulating hormone (TSH) ^a
Hemoglobin	Thyroxine (T ₄) ^b
Microscopy (if positive for blood or protein)	Follicle stimulating hormone (FSH) ^c
Viral serology	
Human immunodeficiency virus (HIV I and II)	Human beta chorionic gonadotrophin
Hepatitis B surface antigen (HBsAg)	
Hepatitis C Virus antibody	

^a Screening only

^b Reflex only (if TSH is abnormal)

^c Screening for post-menopausal women

NB. In case a subject shows an AST **or** ALT $\geq 3 \times \text{ULN}$ together with total bilirubin $\geq 2 \times \text{ULN}$ refer to [Appendix C](#) 'Actions required in cases of increases in liver biochemistry and evaluation of Hy's Law', for further instructions

Urine will be tested for alcohol and cotinine (screening only) and the following drugs of abuse: amphetamines (includes methamphetamines and ecstasy/3,4-methylenedioxymetamphetamine), barbiturates, benzodiazepines, cannabinoids (includes tetrahydrocannabinol), cocaine metabolites, methadone, tricyclic antidepressants, opiates (includes heroin, codeine, and oxycodone), and phencyclidine.

8.2.2 Testosterone, Luteinizing Hormone, Follicle Stimulating Hormone, and inhibin B assessments

In order to monitor for effects on testicular function in male subjects, samples for assessment of testosterone, luteinizing hormone (LH), FSH, and inhibin B levels will be collected at 0 hour (0800 or 1000) and at 4, 6, 8, 12, 22, and 24 hours on Day -1 and at 0 hour (0800 or 1000) and at 1, 2, 4, 6, 8, 12, 24, 36, 48, and 72 hours on Day 1, as listed in the SoA ([Table 2](#)). The results of these assessments will be taken into account at dose escalation meetings, prior to selecting the dose for the next cohort.

8.2.3 Physical examinations

A complete physical examination will be performed and include an assessment of the following systems: cardiovascular, chest/lungs/respiratory, gastrointestinal, thyroid/neck, lymphatics, dermatological/skin, musculoskeletal/extremities, neurological, and head/ears/eyes/nose/throat (including mouth).

Physical examination will be performed at timelines as specified in the SoA. Investigators should pay special attention to clinical signs related to previous serious illnesses; new or worsening abnormalities may qualify as AEs; see [Section 8.3.7](#) for details.

8.2.4 Vital signs

Body temperature, pulse rate (PR), respiratory rate, and BP will be assessed.

Vital signs will be measured in a semi-supine position after 5 minutes rest. Supine and standing BP and PR will be measured using a semiautomatic recording device. Supine BP and PR should be taken after at least 5 minutes supine rest. Standing BP and PR should be taken approximately 3 minutes after the respective supine measurements. Three consecutive BP readings will be recorded at intervals of at least 1 minute. The average of the 3 BP readings will be recorded on the CRF.

Respiratory rate will be measured in breaths per minute by observation at the times indicated in the SoA ([Table 1](#) and [Table 2](#)).

8.2.5 Electrocardiograms

For the timing of ECG assessments, see the SoA ([Table 1](#) and [Table 2](#)) and [Table 12](#).

Twelve-lead paper ECG (pECG) allows the PI to review the ECG tracings at bedside and determine any potential risks. Digital 12-lead ECGs are collected and electronically submitted to the AstraZeneca ECG Center for expert review and reporting of ECG intervals. Telemetry is used for continuous monitoring of ECG activity as a safety measure.

8.2.5.1 Resting 12-lead ECG

Twelve-lead pECGs will be obtained after the subject has been resting in the supine position for at least 10 minutes. All pECGs will be evaluated for HR, and for PR, RR, QRS, QT, and QTcF intervals, and the Investigator will judge the overall interpretation as normal or abnormal. If abnormal, it will be decided whether or not the abnormality is clinically significant or not clinically significant, and the reason for the abnormality will be recorded. The date/time, physician interpretation (normal, abnormal clinically significant, abnormal not clinically significant), and all evaluated parameters and intervals will be recorded in the eCRF, and the paper printouts will be stored at the site.

The PI or delegate will evaluate the printout of the pECG in real time, and with particular attention to the effects of clinical importance on the PR, QRS, and QTcF intervals.

8.2.5.2 Electronic capture and analysis of 12-lead digital ECGs

The AstraZeneca ECG Center will perform the digital ECG (dECG) analysis and interpretation in this study, using the EClysis[®] system, version 4.0, or higher.

Continuous 12-lead dECG recordings will be performed using the site's Mortara Telemetry Surveyor equipment. At CSP-indicated time points in [Table 12](#), 12-lead continuous dECG files will be extracted over at least 5 minutes from the Mortara Telemetry Surveyor continuous files and transmitted to the AstraZeneca central dECG repository, according to AstraZeneca ECG Center's standard procedures, settings, recording, and transmission of dECGs.

Table 12 SAD single dose time schedule for digital electrocardiogram assessments in D7460C00001 during the residential period

Study Days	ECG Number	Time-point	Start Time hour:min ^{a,b}	Dose	Stop Time	dECG cont. ^{c,d,e}	Other ^f
1			-01:30		-01:00		Apply the electrodes ^d
1			-00:40		-00:30		Rest in bed
1	1	Pre-dose	-00:30	Predose	-00:20	10 minutes	
1			-00:20		-00:05		Toilet use recommended
1			00:00	IP Admin			
1	2	30 min	00:25		00:30	5 minutes ^e	
1	3	1 h	00:55		01:00	5 minutes ^e	
1	4	1.5 h	01:25		01:30	5 minutes ^e	
1	5	2 h	01:55		02:00	5 minutes ^e	
1	6	3 h	02:55		03:00	5 minutes ^e	
1	7	4 h	03:55		04:00	5 minutes ^e	
1	8	6 h	05:55		06:00	5 minutes ^e	
1	9	8 h	07:55		08:00	5 minutes ^e	
1	10	12 h	11:55		12:00	5 minutes ^e	
2	11	24 h	23:55		24:00	5 minutes ^e	
2	12	36 h	35:55		36:00	5 minutes ^e	
3	13	48 h	47:55		48:00	5 minutes ^e	
4	14	72 h	71:55		72:00	5 minutes ^e	

^a Time points for dECG may be adjusted according to emerging PK data.

^b Times are approximate as dECG and safety ECGs need to be completed before blood sampling.

^c The subject must be in the same supine body position (max. 30 degrees flexion in the hip) at each time point and at all visits. Subject's feet should not contact the footboard of the bed.

^d Skin must be cleaned, and electrode positions marked with an indelible pen. Electrodes should be applied at least 30 minutes before first recording.

^e Subject must rest in bed for at least 10 minutes prior to each ECG time point.

^f On the dosing days, safety ECG will be printed at the end of each dECG extraction window.

dECG Digital electrocardiogram; ECG Electrocardiogram; IP Investigational product; PK Pharmacokinetics; SAD Single ascending dose

The same recording device will be used for each subject at all time points, when possible.

Date and time settings must be checked on the Mortara Telemetry Surveyor at the start of each study day and aligned with an official timekeeper.

Skin preparation must be thorough and electrode positions must be according to standard 12-lead ECG placement.

Electrode positions will be marked with an indelible pen at the start of each study day to ensure exact reposition. Permanent electrodes will be applied at least 30 minutes before first study recording and left in place for the duration of each relevant study day.

Subjects will rest in a supine position for at least 10 minutes (can be reduced to 5 minutes at collection time points within the first hour after dosing) before the start of each recording. The subject should be in the same supine body position (maximum 30 degrees flexion of the hip and feet not in contact with the footboard) at each recording time point during the study.

The metadata for all dECG files will be checked by the responsible personnel at the study site to ensure that the files transferred to the AstraZeneca central dECG files repository can be approved by the AZ ECG Center to be made accessible to the ECG Scientific Advisors for analysis. As a standard, 10-second ECGs will be extracted by the EClysis[©] system twice per minute from the continuous recording and initially automatically analyzed by the software.

Lead V2 will be analyzed and reported as primary. Lead V5 will be analyzed, for all visits, as backup for the individual where analysis in lead V2 is not deemed possible for pre-dose, for significant parts of visits or for whole visits.

The ECG Scientific Advisor will perform all required manual corrections to the ECG annotations provided automatically by EClysis[©].

To provide a decision basis for dose escalation, the ECG Scientific Advisor(s) will perform a preliminary analysis of the first 24 hours of dECG recordings in lead V2, with the main focus on QT changes, wave morphology changes, and dysrhythmia.

The AZ ECG Center Cardiologist will review the data, perform an evaluation and interpretation of the findings, and will provide a safety report for the SRC meeting.

The AZ ECG Center Cardiologist will review the totality of the data and perform all necessary adjustments before locking the EClysis[©] data into a read-only state, before the data will be exported.

The numerical values for ECG intervals and amplitudes will be exported and made accessible on the AstraZeneca dECG Central repository to accredited data management specialists for conversion into SAS[®] files.

The following dECG variables will be reported by the AstraZeneca ECG Center: RR, PR, QRS and QT intervals from the lead defined as the primary analyses lead. Derived parameters (QTcF, HR, and others, as applicable) are calculated by the study statistician or delegate.

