7 DISCONTINUATION OF TREATMENT AND SUBJECT WITHDRAWAL

7.1 Discontinuation of study treatment

As individual subjects are given only one dose of IP, there are no criteria for discontinuing study treatment. This section describes the criteria for study termination and the discontinuation of planned dose escalations within the study.

The sponsor designee reserves the right to close the study site or terminate the study at any time for any reason at the sole discretion of the sponsor.

The study may be stopped if, in the judgement of AstraZeneca, trial subjects are placed at undue risk because of clinically significant findings that:

- Meet individual stopping criteria or are otherwise considered significant
- Are assessed as causally related to IP
- Are not considered to be consistent with continuation of the study

Regardless of the reason for termination, all data available for the subject at the time of discontinuation of follow-up must be recorded in the CRF.

In terminating the study, the sponsor will ensure that adequate consideration is given to the protection of the subjects' wellbeing.

After each cohort, an SRC will review and assess all the available safety and PK data from all of the cohorts to date in order to make a decision on the dose for the next cohort of subjects.

Data from a minimum of 6 subjects dosed per cohort must be reviewed before each dose escalation.

If any of the following scenarios occur within a cohort with a reasonable possibility of a causal relationship with AZD4041, escalation to the next, higher dosage level may not occur:

General

- One or more subjects, who receive AZD4041, report a SAE or experience AEs judged to be non-tolerable by the PI or the SRC, and are deemed related to AZD4041.

Cardiovascular criteria

- Two or more subjects, who receive AZD4041, have QTc prolongation defined as QTcF >500 ms, or a prolongation from baseline of >60 ms, confirmed (persistent for at least 5 minutes) and determined post-dose either during continuous 12-lead ECG monitoring or on a repeat 12-lead ECG.
- Two or more subjects, who receive AZD4041, have tachycardia defined as resting supine HR >125 beats per minute persisting for at least 10 minutes.
- Two or more subjects, who receive AZD4041, have symptomatic bradycardia defined as resting supine HR <40 beats per minute or asymptomatic bradycardia defined as resting supine HR <30 beats per minute while awake and persisting for at least 10 minutes.

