- Two or more subjects, who receive AZD4041, develop hypertension defined as an increase in resting supine systolic BP >40 mmHg to above 180 mmHg and persisting for at least 10 minutes.
- Two or more subjects, who receive AZD4041, develop hypotension defined as an asymptomatic fall in systolic BP of >20 mmHg to <70 mmHg persisting for at least

10 minutes, or a symptomatic fall in resting supine BP >20 mmHg (excluding vasovagal reaction).

- Two or more subjects, who receive AZD4041, have tachycardia defined as resting supine heart rate >125 beats per minute persisting for at least 10 minutes.
- Two or more subjects, who receive AZD4041, have a non-sustained ≥ 5 beat if “slow” (<100 bpm), or “fast” (≥ 100 bpm) ventricular tachycardia.
- One or more subjects, who receive AZD4041, have a sustained ventricular tachycardia (ie, >30 second duration, or leading to hemodynamic consequences requiring immediate arrhythmia termination).

Laboratory findings

- One or more subjects, who receive AZD4041, fulfill Hy’s Law defined as “An increase in aspartate aminotransferase (AST) or alanine aminotransferase (ALT) ≥ 3 x upper limit of normal (ULN) and total bilirubin (TBL) ≥ 2 x ULN, where no other reason can be found to explain the combination of increases; eg, elevated serum alkaline phosphatase (ALP) indicating cholestasis, viral hepatitis, or another drug.” The elevations do not have to be at the same time or within a specified time frame.
- Two or more subjects, who receive AZD4041, have >3 x ULN of either ALT or AST, or >2 x ULN for TBL or ALP.

Criteria for halting dose escalation

PK data indicate that the predefined maximum exposure level/maximum plasma concentration (free C_{max} of [REDACTED])

[REDACTED] has been achieved, or is predicted to be achieved or exceeded should the dose be increased as planned. The exposure limits should be applied on mean values within a cohort. If this halting dose escalation criterion is met, the SRC will stop any further dose escalation. The SRC will determine whether a lower or the same dose should be tested or whether the study should be terminated.

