8.6.2. Digital ECG

The AstraZeneca ECG Center will perform the digital ECG (dECG) analysis and interpretation in this study, using the EClysis[®] system, version 4.0, or higher. The following dECG variables will be reported by the AstraZeneca ECG Center: RR, PR, QRS and QT intervals from the lead defined as the primary analyses lead. Heart rate will be derived as 60/(RR in seconds) and QTcF will be derived as QT (msec)/(RR in seconds)^{1/3}.

The dECG data will be smoothed on an individual subject basis before performing the derivations above and before calculation of any changes from baseline or descriptive statistics. For each subject it will be done as follows: the mean value of all the measurements will be taken for nominal time-point recordings. At least 4 measurements with the time between the first and last record greater than 2.75 minutes for a nominal time-point should be present or else, the smoothed value at the corresponding nominal time-point will be set to missing.

Digital ECG results will be listed by treatment (pooled placebo, dose level of AZD4041) for each subject and time-point and will include all individual and smoothed values of PR, RR, QRS, QT interval and the derived values of QTcF and HR. The changes from baseline for smoothed and derived parameters will be listed as well.

Descriptive statistics of smoothed PR, RR, QRS, QT values and derived QTcF and HR values as well as change from baseline will be summarized by treatment group (pooled placebo, dose level of AZD4041, and pooled AZD4041) and nominal time-point. The baseline for the dECG measurements will be the smoothed pre-dose assessment on Day 1.

The number and percent of subjects whose worst (i.e. highest) post-baseline smoothed QTcF value, according to the following categories, will be tabulated by visit, timepoint, and treatment group (pooled placebo, dose level of AZD4041, and pooled AZD4041):

- Absolute value >450 msec and ≤ 480 msec
- Absolute value >480 msec and ≤ 500 msec
- Absolute value >500 msec
- Increase from baseline >30 msec and ≤ 60 msec

- Increase from baseline >60 msec

The above tabulations will be presented separately for the subgroups who have an elevated QTcF (>450 msec) at baseline and those who do not.

All dECG data will be presented in a listing.

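### The central digital-ECG read that feeds dose escalation stops at 24 hours, so the 36, 48 and 72 h recordings need no central read before the next dose level

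*Protocol*

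**What the plan says.** Protocol section 8.2.5.2 describes three steps of central dECG review.

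- The preliminary read, in lead V2: "To provide a decision basis for dose escalation, the ECG Scientific Advisor(s) will perform a preliminary analysis of the first 24 hours of dECG recordings".
- The ECG Center cardiologist then reviews the data and "will provide a safety report for the SRC meeting". No time window is given for this report.
- Before export, the cardiologist is to "review the totality of the data and perform all necessary adjustments before locking" the EClysis data. This step is linked to the lock and not to escalation.

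Table 12 schedules dECGs from pre-dose to 72 h; the 72 h recording applies to Cohorts 4 to 6.

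Other parts of the plan have a wider reach. Under section 7.1, after each cohort "an SRC will review and assess all the available safety and PK data from all of the cohorts to date". The QTcF criterion there counts prolongation that is "confirmed (persistent for at least 5 minutes) and determined post-dose either during continuous 12-lead ECG monitoring or on a repeat 12-lead ECG", and another criterion reads "One or more subjects, who receive AZD4041, have a sustained ventricular tachycardia"; neither has a time limit. Section 8.4.6 lists eight items for the SRC, including a dECG safety report, and covers data through Day 15 so far as they are available. SAP section 8.6.2 will tabulate subjects "whose worst (i.e. highest) post-baseline smoothed QTcF value" falls in set categories.

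**The concern.** The one central read whose stated purpose is to support escalation covers a shorter period than the criteria it serves and the data the SRC reviews. It also stayed at 24 h although Protocol section 2.2.2 extends human telemetry to 48 h because of the dog arrhythmia finding. No reason is given for the difference.

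What may be missing when the next dose is chosen is the better measurement of late intervals. The plan treats the dECG as its main interval measurement: SAP section 8.6.2 summarizes it, while section 8.6.1 only lists the paper ECG. Each dECG extract yields several manually corrected ECGs over at least 5 minutes, whereas no replicates are described for the paper tracing.

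There is some reason to think the late recordings carry information. Protocol section 2.3 reports that in Cohort 3, sampled to 48 h, three subjects had more than 20% of AUC0-inf extrapolated, so appreciable drug remained well after 24 h. That does not show a late QT effect.

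**Working it through.** The plan gives no figure of its own on this point. The check is a reading of the text plus counts from Table 12, section 8.2.5.2 and the cohort size (6 active, 2 placebo).

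**Time points outside the read**
- Post-dose dECGs in Table 12: 0.5, 1, 1.5, 2, 3, 4, 6, 8, 12, 24, 36, 48 and 72 h = 13.
- Within 24 h: 10. After 24 h: 3.
- Share outside: 3/13 = 23% in Cohorts 4 to 6. Without the 72 h point (Cohorts 1 to 3) it is 2/12 = 17%.
- The Schedule of Activities ties ECGs to the PK times, which add 0.25 h. On that count the share for Cohorts 4 to 6 is 3/14 = 21%.

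**Recordings per cohort**
- AZD4041: 6 × 3 = 18. These are the subjects the escalation criteria count.
- Placebo: 2 × 3 = 6.
- Total: 24.

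**Reading load**
- Ten-second ECGs are extracted "twice per minute from the continuous recording", so a 5-minute extract gives 5 × 2 = 10 and the 10-minute pre-dose extract gives 10 × 2 = 20.
- Present 24 h read: 8 × (20 + 10 × 10) = 8 × 120 = 960 ECGs. All eight subjects are included because review starts blinded.
- Late recordings: 24 × 10 = 240 ECGs.
- Increase: 240/960 = 25%.

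**Timing**
- The 72 h recording is 3 days post-dose. Follow-up is at 14 ± 2 days.
- The gap is 14 − 3 = 11 days, with a range of 12 − 3 = 9 to 16 − 3 = 13 days.

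**Decisions affected**
- Section 2.3 has Cohort 4 complete and Cohort 5 at 5 of 8 subjects. The planned decision still ahead is Cohort 5 to 6.
- Under Table 2, note f, those first five Cohort 5 subjects had scheduled telemetry only to 24 h. The other three have it to 48 h.

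**Does any text require the later read before escalation?** The section 8.4.6 report item has no minimum window, and the data are reviewed only as available. The cardiologist's report in section 8.2.5.2 has no window either. Both permit a read of the later recordings; neither requires it.

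**The case against.** The strongest reply is that this is a preference and not a gap. The 24 h limit applies only to a preliminary step. The cardiologist's report and the SRC's dECG item carry no such limit, and section 4.3 places the details of the data required for escalation in the SRC Charter. The stopping rules do not depend on the central read: the QTcF rule can be met on continuous monitoring or a repeat ECG, and ventricular tachycardia is better caught by telemetry than by short extracts. The SAP categories belong to the final report, and an interim look narrower than the final analysis is normal. The dog ectopy ran from about 7 h to 24 h after dosing, inside the window, and section 2.2.2 does not expect QT prolongation.

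Much of this stands. Late changes would not go unseen: paper ECGs at 36, 48 and 72 h are read in real time under section 8.2.5.1, and their intervals reach the SRC. No late QT effect has been shown, and the documents give no basis for sizing one that might be missed. The Charter may settle the matter.

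Two things remain. The 24 h limit is a stated rule, so a Charter that asks for more would still leave section 8.2.5.2 saying 24 hours. And scheduled telemetry does not reach 72 h in any cohort.

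It is also fair to say that reading what is available at the data cut would change nothing if the SRC met before the late recordings had been processed.

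**Conclusion.** The point holds and is minor. As written, the protocol does not require a central read of 3 of the 13 post-dose time points (23%) before escalation in Cohorts 4 to 6: 24 recordings per cohort, 18 of them on AZD4041. One planned decision is affected, plus any repeated or added cohort. The change is a cheap improvement and does not repair an unmonitored risk.

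Confidence is medium, because the SRC Charter could not be seen and may already require the later read. The counts assume full cohorts of eight, extracts of exactly 5 minutes (the protocol sets this as a minimum), and the Table 12 schedule unchanged; its notes allow times to be adjusted to emerging PK data.

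**What to change.** In Protocol section 8.2.5.2, replace the 24-hour limit on the preliminary read with: *all Table 12 dECG recordings available at the SRC data cut (through 72 h for Cohorts 4 to 6)*. State the same range in the dECG safety-report item of section 8.4.6. If the Charter already requires this, the sponsor need only say so and align section 8.2.5.2 with it.

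The cost is a wording change and about 240 ten-second ECGs per cohort read before the SRC meeting instead of before lock, on top of about 960. The recordings are already scheduled and must be reviewed before lock in any case, so no new procedure or visit is needed. If the SRC meets after follow-up, the 9 to 13 days since the 72 h recording should be enough for the read. That is an assumption, because the documents give neither an ECG Center turnaround time nor a fixed SRC date. If the SRC meets earlier, the wording does not oblige it to wait.
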